2. PROTOCOL SYNOPSIS

Study design	Randomized, open-label, multi-centre study to evaluate the tolerability of the application of a combination of a serum containing human bone marrow stem cell derived growth factor and cytokines (SCR Complex™) and a botanical lipid based occlusive (Bio Cel™) following facial fractional RF treatments using the Venus Viva™ SR system. Each subject will receive 2 treatments separated by a 3-week interval. Subjects will complete a VAS and Tolerability Scale immediately following each treatment. Telephone follow-up calls by the site will ask the subject to respond to the Self-Report Adverse Event Questionnaire 24 and 72 hours after the first treatment and 24 hours after the second treatment. Subjects will complete a Home Tolerability Scale 24 and 72 hours after the first treatment and 24 hours after the second treatment. Subjects will return for the final FU visit and be asked to respond to the Self-Report Adverse Event Questionnaire and complete the Home Tolerability Scale for 72 hours. The investigator will also evaluate the subject's improvement using the GAIS at this visit.
Study center / country	2 Study Centres; USA
Study duration	1) For each subject, study duration will be approximately 30 days, including study follow-up. 2) Anticipated start date: July 2016; Anticipated stop date: September 2016.
Investigational product	Venus Viva™ SR system is intended for dermatological procedures requiring ablation and resurfacing of the skin. SCR Complex™ contains human growth factors and cytokines derived through laboratory culture of human bone marrow mesenchymal stem cells. It is indicated for use immediately following and for the first few days of the acute healing phase after treatment with the Venus Viva™ device. Bio Cel™ is a botanical lipid-based gel occlusive. It is indicated for use as an occlusive barrier following ablative and semi-ablative skin treatments, regardless of modality.
Planned number of participants	A total of up to 100 evaluable male or female subjects (Fitzpatrick Skin types I – VI) will be enrolled. Subjects will present with acne scars, general skin texture irregularities and/or rhytides.
Study objectives	Clinical evaluation of the tolerability of using a post-treatment topical adjuvant combination immediately following RF fractional ablation using the Venus Viva™ SR system.

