6. PRIMARY ENDPOINT

The primary outcome measure will be the tolerability of the application of the stem cell recovery complex (SCR Complex™) and a botanical lipid based occlusive (Bio Cel™) as compared with standard of care following fractional RF treatments.

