11.2 Treatment Visits

Subjects that did not experience significant pain or skin sensitivity in response to the test spots can receive treatments. Each subject will be enrolled and scheduled for two treatments, three weeks apart and return for a follow-up visit three days after the second treatment for evaluation of the treatment area.

The following procedures and assessments are required at the treatment visits:

Pre-treatment

- Confirm continued eligibility regarding inclusion/exclusion criteria
- Review any changes in medication, health status or AE from last visit
- Assessment of adverse events including a photograph of the affected treatment area if an adverse event occurred
- Assessment of concomitant medications
- Assign randomized treatment (after 1st treatment visit only)
- Apply a topical anesthetic preparation over the treatment areas, if required. (If used, record in the CRF.)

Treatment

No lotion, gel or coupling medium is to be used in this treatment. The distal part of the applicator should be clean and dry before fitting it with a new 160 pins tip. The skin in the treated area should also be cleaned well (for removal of any lotions, make-up residues, topical anesthetic cream, etc.) and patted dry. Hairs that exist in the areas should be shaved off.

- Treatment should be performed while the subject is lying down comfortably; the operator should have easy access to the subject's treatment area.
- Areas of dental crowns, caps, braces, or other metal dental implants may be more sensitive to treatment and the clinician may use dental rolls, gauze or a tongue depressor to isolate the area and make the treatment more comfortable (if the face is treated).
- Treatment of subjects in hair-bearing areas may result in some damage to the follicles and subsequent loss of hair. Avoid the beard area (if face is treated) and other hair growing zones if the patient doesn't wish to have reduction of the hair growth. This treatment may also result in in-grown hairs.
- The applicator should be held perpendicular to and in close contact with the skin.
- Pressing the trigger will release the RF energy to the skin, creating a stamped imprint in a shape and intensity depending on energies.

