- The immediate responses, indicative of the desired effect, are erythema and edema in the immediate area of the stamp and possibly also around it. The edema usually appears 1-2 minutes post-treatment and reaches its peak (of up to moderate edema) within 30 minutes. It should be noted that erythema is not easily noticeable, if at all, in darker skin types, so the edema will indicate a more significant effect in these subjects.
- Treatment consists of a single pass over the designated area.
- Unless otherwise instructed, the energy parameters can be modified between the treatment visits, as per the Investigator's discretion.
- It is recommended that throughout the study, that one staff member administer the treatments and another staff member perform the evaluations of the treatment area.

Post Fractional RF Treatment

- Subject Discomfort Assessment recorded on a 100mm visual analogue scale (VAS) immediately post treatment.
- Subject Tolerability Scale immediately post treatment.
- Subjects will receive either the adjuvant combination treatment (SCR Complex™ followed by Bio Cel™ occlusive gel applied to the treatment area) or SOC (no topical applications to treatment for 24 hours post fractional RF treatment).
- Subjects will be asked to complete the Subject Home Tolerability Scale at 24 hours and 72 hours post-treatment
- Subjects will be provided with the Subject Home Instruction Sheet (Appendix B).
- A follow-up telephone call will be made to the subject 24 and 72 hours after the first treatment and 24 hours after the second treatment. Study staff will ask the subject to report on the treatment using the Self-Report Adverse Event Questionnaire (Appendix C) and remind the subject to complete and return to the clinic with their completed Subject Home Tolerability Scale at each visit.

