14. STATISTICAL CONSIDERATIONS

Statistical Design

This study is a randomized, open-label, multi-centre study.

Sample Size

Enrollment will continue until up to 100 evaluable subjects have been recruited to the study. Any subject removed from the study in accordance with the provisions of this protocol will be replaced by other subject.

Statistical Methods

All subjects who received any amount of treatment will be included in the report. The primary outcome measure is the subject's overall tolerability of the adjuvant combination treatment as compared to the standard of care post fractional RF treatment. The self-assessment will be based on a 5-point Likert scale - Subject Tolerability Scale (Appendix A). Summary statistics will be generated for subject tolerability immediately after treatment, 24 hours and 72 hours following

treatment as per the terms: Very tolerable, tolerable, having no opinion, intolerable and very intolerable.

The secondary outcomes measures are the subject's degree of discomfort and/or pain as measured by the visual analogue scale (VAS), the incidence of spontaneous adverse events (AEs) and the investigator's assessment of improvement using the Fitzpatrick Wrinkle and Elastosis Scale scores before and after treatment as well as Global Aesthetic Improvement Scale (GAIS) for each subject. VAS scores from the treated group will be compared with the VAS scores of the standard of care group. The investigator's assessment of improvement using the Fitzpatrick Wrinkle and Elastosis Scale from the treatment group will be compared with that of the standard of care group. The GAIS scores for both groups will also be compared.

Summary statistics will also be generated for all treatment emergent adverse events (TEAs). The following types will be reported:

- Overall TEAEs
- Severe TEAEs
- TEAEs related to treatment
- Serious Adverse Events (SAEs)
- SAEs related to treatment
- TEAEs leading to treatment discontinuation

15. DATA HANDLING and RECORD KEEPING

Confidentiality

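### At Tx 1 the immediate tolerability score appears to be taken before the topical step, yet it is reported as a primary time point rather than as a baseline

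*Combined protocol and SAP*

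**What the plan says.** Section 6 sets the target: "The primary outcome measure will be the tolerability of the application of the stem cell recovery complex" with its occlusive, against SOC. Section 14 repeats it as "The primary outcome measure is the subject's overall tolerability of the adjuvant combination treatment" versus SOC, on a 5-point scale. It then gives the time points: "Summary statistics will be generated for subject tolerability immediately after treatment, 24 hours and 72 hours following" treatment. None is ranked above another, overall tolerability is not defined further, and no test, model or covariate is named.

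Section 11.2, in the part on what happens after fractional RF, lists these items in order:

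1. the discomfort VAS;
2. "Subject Tolerability Scale immediately post treatment";
3. "Subjects will receive either the adjuvant combination treatment" or SOC;
4. the home scale at 24 h and 72 h.

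The synopsis says only "Subjects will complete a VAS and Tolerability Scale immediately following each treatment", without placing the scale before or after the topical.

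On assignment, the pre-treatment list of Section 11.2 has "Assign randomized treatment (after 1st treatment visit only". Section 8 ties assignment to the subject number, and Section 11.1 gives each subject a unique number at screening. Section 14 describes the trial as open-label: "This study is a randomized, open-label, multi-centre study".

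**The concern.** SOC means no topical for 24 hours (Section 8). If the immediate scale is completed before the topical step, then at Tx 1 both arms have had the same RF procedure and nothing else when they score it. The score then measures how the subject took the RF session, not how the subject tolerated the products.

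Two things are at stake. The first is interpretation. A chance difference at this time point could be read as early benefit or harm of the adjuvant, and a null could be read as no immediate benefit. Neither reading would be justified. The second is precision. A same-scale score taken just before exposure is a natural covariate for the 24 h and 72 h scores. It may well be informative, because RF settings vary by skin type and intensity (Table 1) and anaesthetic is optional. The plan collects it but gives it no such role.

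**Working it through.** **No plan figure to reproduce.** Section 14 gives up to 100 evaluable subjects, with no alpha, power, effect size or SD. Everything numerical below rests on assumptions: 50 per arm (1:1 is not stated), two-sided 0.05, normal approximation, equal SDs, and a common correlation r of 0.3, 0.5 or 0.7 between time points.

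**Step 1: the order.** The bullets are not numbered. However, the blocks of Section 11.2 run pre-treatment, treatment, post-treatment, and the post-treatment block ends with the later scores, so it reads chronologically. The footnotes to the Schedule of Events label the in-clinic score as time 0. Nothing in the document places it after the topical.

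**Step 2: when the arm is known.** The assignment bullet sits among the pre-treatment items but is worded as following the first treatment visit. Taken literally, that would leave no arm to apply at Tx 1. If the subject number of Section 8 is the number given at screening, the arm could be fixed, and perhaps known, from the start. The documents do not settle this.

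**Step 3: what chance alone does to the Tx 1 immediate score.** The SE of the arm difference is √(2/50) = 0.20 SD. The 95% range around zero is ±1.96 × 0.20 = ±0.39 SD.

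**Step 4: value as a covariate at one later time point.** Residual variance is 1 − r². The detectable difference at 80% power is (1.960 + 0.842) × 0.20 × √(1 − r²). Power for a true 0.5 SD effect is Φ(0.5 / [0.20 √(1 − r²)] − 1.96).

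| r | Variance removed | Detectable difference | Power at 0.5 SD |
|---|---|---|---|
| unadjusted | 0 | 0.56 SD | 70.5% |
| 0.3 | 9% | 0.53 SD | 74.6% |
| 0.5 | 25% | 0.49 SD | 82.3% |
| 0.7 | 49% | 0.40 SD | 93.8% |

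These figures belong to a linear model on the 0 to 4 scores. In a proportional-odds model the gain appears as power, and the odds ratio is conditional on the baseline score.

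**Step 5: only if the three Tx 1 scores were averaged.** With an effect d at 24 h and 72 h and none at the immediate score, the mean effect is (0 + d + d)/3 = 2d/3, a loss of one third. The variance of the mean is (1 + 2r)/3, so relative information is (4/9) × 3/(1 + 2r) = 4/[3(1 + 2r)]: 0.833, 0.667 and 0.556 for the three values of r. The plain 24 h/72 h mean has 2/(1 + r): 1.538, 1.333 and 1.176. The ratios are 54%, 50% and 47%.

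**The case against.** A reader might infer that the plan dilutes its primary result toward no difference. The documents do not support that as a fact. Section 14 promises summaries at each time point by response category. It specifies no mean, composite or pooled test, so a null immediate score would leave the 24 h and 72 h tables untouched. Step 5 shows what would follow from one possible meaning of overall tolerability, not what is planned.

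A reader might also infer that the Tx 1 immediate score cannot differ by arm, or that it is already a clean baseline. That too is stronger than the text. The order comes from unnumbered bullets, and the misplaced assignment item shows that list position is not a fully reliable guide to timing. The synopsis describes the topical as applied immediately after RF as well, so both steps are immediate. If subjects know their arm before scoring, expectation can move a subjective rating. Adjusting for a score affected in that way could distort the comparison.

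Finally, the plan is descriptive, so no stated power or error rate is damaged, and a by-arm table of the immediate score would already show comparability. All of this stands, and it narrows the point. It does not justify presenting, as a primary outcome, a score that on the natural reading precedes the intervention.

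**Conclusion.** The point holds in a limited form. On the natural reading of Section 11.2, the Tx 1 immediate score precedes the adjuvant or SOC step and cannot reflect a product effect, while Section 14 reports it as primary outcome data. Differences of up to about 0.39 SD would be unremarkable by chance at 50 per arm. If the score is recorded before the arm is disclosed, using it as a covariate would remove roughly 9% to 49% of the variance at a later time point. That range is only as good as the assumed correlations of 0.3 to 0.7, which the documents neither give nor contradict.

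The argument is confined to Tx 1. At Tx 2 the immediate score follows the first session's adjuvant exposure, so it may carry an effect of it and is not a baseline.

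**What to change.** - **Section 11.2:** state that at Tx 1 the immediate scale is completed after RF, before the arm is disclosed and before any topical. Reword the assignment item so that its timing agrees with this and with Section 8. The discomfort VAS is also listed before the topical step, so the same sentence should cover it.
- **Section 14:** show the Tx 1 immediate score by arm as a baseline. Make 24 h and 72 h the primary between-arm comparison, and say which treatment session feeds it. Adjust for the Tx 1 immediate score, for example in a proportional-odds model for the 5-point scale. State that the Tx 2 immediate score is not used as a baseline.
- **If the arm must be disclosed before scoring:** do not use the score as a covariate, and still leave it out of the primary comparison.

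No new data, visits or forms are needed. The costs are that sites must withhold the arm at Tx 1 until the score is recorded, and that one model is added to a plan that is otherwise descriptive.

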11.3 Follow-up/Termination Visit

Subjects will be scheduled for a follow-up/termination visit 72 hours after the second treatment. The following procedures will be performed:

- The subject will be asked to report on the comfort(s)/discomfort(s) associated with the second treatment as per the Self-Report Adverse Event Questionnaire.
- Wrinkle evaluation (Fitzpatrick Wrinkle and Elastosis Scale)
- Global Aesthetic Improvement (GAI) Scale (Appendix D) as evaluated by the investigator.
- Subject Tolerability Scale 72 hours post second treatment
- Assessment of concomitant medications

The subject's participation in the study is now complete. In case of early termination, the date and reason for early termination will be recorded in the CRF. Subjects will also be asked to return to the clinic to complete follow-up/termination visit procedures.

12. SAFETY ASSESSMENT

Adverse Events Definitions

In this study, an Adverse Event (AE) is any undesirable clinical occurrence (sign, symptom, illness, or other medical event), that appears or worsens during the clinical study, or requires medical treatment or intervention to a subject, whether it is considered to be device related or not. If an adverse event occurs, the first concern will be the safety and welfare of the subject. Appropriate medical intervention will be made.

Any AE or complication reported by the subject or observed by the physician that occurs during or after treatment with the device will be recorded in the subject's medical record or source document and on the Adverse Event Case Report Form. The investigator will determine if the AEs are device related or procedure related. This assessment shall include the onset date, resolution date, severity, seriousness, frequency, treatment and outcome.

Each AE should be assessed according to the following criteria:

Severity

Each AE should be assessed for its severity, or the intensity of an event experienced by the subject.

Mild: Awareness of a sign or symptom that does not interfere with the subject's activity or is transient resolved without treatment and has no sequelae.

Moderate: May interfere with the subject's usual activity and require additional intervention and/or treatment, and may have additional sequelae.

Severe: Significant discomfort to the subject and/or interferes with the subject's activity. Additional intervention and or treatment are necessary. Additional sequelae occur. Severe is used to describe the intensity of an event experienced by the subject.

Adverse Device Effect (ADE)

Each AE should be assessed for its relationship to the device or procedure as identified as follows:

Device: This category should be restricted to adverse events directly attributable to the effect of the device.

Procedure: A procedure is any activity that supports the usage of the device.

Use the following categories for assigning the certainty of the relatedness:

Related: The AE is known to occur with the study agent, there is a reasonable possibility that the study agent caused the AE, or there is a temporal relationship between the study agent and event. Reasonable possibility means that there is evidence to suggest a causal relationship between the study agent and the AE.

Not Related: There is not a reasonable possibility that the administration of the study agent caused the event, there is no temporal relationship between the study agent and event onset, or an alternate etiology has been established.

Pre-existing Conditions

A pre-existing condition should not be reported as an adverse event unless there has been a substantial increase in severity or frequency of problems, which has not been attributed to natural history.

Diagnosis of Adverse Event

There should be an attempt to report a “diagnosis” rather than the individual signs, symptoms and abnormal laboratory values associated with the diagnosis. However, a diagnosis should be reported only if, in the Investigator’s judgment, it is relatively certain (i.e., definite or possible). Otherwise individual signs, symptoms and abnormal laboratory values should be reported as the adverse events.

Anticipated Outcome Related Adverse Events

Anticipated adverse events in this study may include: temporary minor skin irritation, redness or swelling which may last from a few minutes to a few hours, minor swelling in the treated area for up to a week or slight heat discomfort during treatment. Very rarely, there may be possible bruising, burns, hyperpigmentation (skin turns darker) or hypopigmentation (skin turns lighter).

Any anticipated AE that occurs at any time during or after the use of the study device must be reported by the Investigator to Venus Concept. If the anticipated AE, in the opinion of Venus Concept or the Investigator, is likely to affect the safety of the subjects or the conduct of the study, the Research Ethics Board (REB)/Institutional Research Board (IRB) will be notified of the event within 10 working days after Venus Concept first receives notice of it.

Unanticipated Adverse Device Effects (UADE)

An unanticipated adverse device effect as defined by the Federal Regulations [21 CFR 812.3(s)] as “any serious adverse effect on health or safety or any life-threatening problem or death caused by, or associated with, a device, if that effect, problem, or death was not previously identified in nature, severity, or degree of incidence in the investigational plan or application (including a supplementary plan or application), or any other unanticipated serious problem associated with a device that relates to the rights, safety, or welfare of subjects.” From a practical perspective, an unanticipated adverse device effect means a serious adverse event that is not listed in the device labeling, or the frequency or severity is greater than reported in the device labeling.

In the event of a serious (or unanticipated) adverse event, the Investigator will immediately notify the Venus Concept monitor by telephone. If such an adverse event is being reported after normal working hours, the Investigator will leave a voice message with an accompanying report of the AE. If the unanticipated AE, in the opinion of Venus Concept or the Investigator, is likely to affect the safety of the subjects or the conduct of the study, the IRB/ Helsinki/ other ethic committee will be notified of the effect within 10 working days after Venus Concept first receives notice of it.

Serious Adverse Event (SAE)

NOTE: The term serious is not synonymous with severity, which may be used to describe the intensity of an event experienced by the subject. An AE that does not meet any of the below criteria will be classified as non-serious.

A serious AE is any event that:

- Results in, or contributes to a death;
- Is immediately life-threatening (injury or illness);
- Results in hospitalization, or prolongs an existing hospitalization;
- Results in permanent impairment of body structure or function, or in persistent or significant disability/incapacity;
- Results in an injury that requires medical intervention to prevent permanent impairment of body structure or function;
- Is a device malfunction or deterioration in the characteristics and/or performance of the device that results in death or serious deterioration in health;
- Is a device malfunction or deterioration in the characteristics and/or performance of the device that, if it were to occur again, could result in death or serious deterioration in health;
- Results in a congenital anomaly or birth defect;
- Is any medically significant injury, event or experience that requires medical/surgical intervention to prevent one of the outcomes listed above;
- Results in end-organ toxicity, including hematological, renal, cardiovascular, hepatic, gastrointestinal, and central nervous system events.

Reporting

Adverse Events (AE) and Serious Adverse Events (SAE) Reporting

All serious AEs, whether or not deemed expected or device-related, must be reported to the clinical monitor immediately or within 24 hours by telephone (see below). A written report must follow within five (5) working days and is to include a full description of the event and sequence. If the Venus Concept monitor cannot be reached, the site personnel will directly contact [name], Director of Clinical Research at [contact] or designate.

In addition to reporting adverse events within the context of this clinical study, any applicable local device reporting requirements will be followed.

Device Malfunctions

All investigational device malfunctions will be documented on the CRF and reported in the clinical results. Devices that malfunction during the procedure will be returned to the sponsor for analysis.

Device Malfunction: A device malfunction means the device did not meet its performance specifications, including specifications in the labeling, or otherwise perform as intended.

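### Adverse event causality is assessed against the RF device and the procedure only; the randomised topical products are not named as a target, and the related-event tables leave 'treatment' undefined

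*Combined protocol and SAP*

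**What the plan says.** Section 8 (Randomization) allocates subjects to SCR Complex plus Bio Cel or to standard of care, meaning no topical for 24 hours. Both groups have the same RF procedure. Section 6 makes the primary endpoint the "tolerability of the application of the stem cell recovery complex" together with Bio Cel, compared with standard of care.

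Section 12 handles causality in three steps:

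- It states the task: "The investigator will determine if the AEs are device related or procedure related".
- It repeats this under Adverse Device Effect: "Each AE should be assessed for its relationship to the device or procedure as identified as follows". Two targets follow: "Device: This category should be restricted to adverse events directly attributable to the effect of the device" and "Procedure: A procedure is any activity that supports the usage of the device".
- It then gives a Related / Not Related scale worded around a different object: "The AE is known to occur with the study agent, there is a reasonable possibility that the study agent caused the AE", or a temporal relationship exists between the two. The term is not defined.

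Section 14 lists six safety summaries. One is "TEAEs related to treatment" and another is the matching SAE summary. Section 14 does not define treatment in this context. The Synopsis (Statistical Methodology) adds that TEAEs will be presented for the treatment group and the standard of care group.

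**The concern.** The trial asks how well a topical combination is tolerated after RF. A reader of its safety report will want to know which events investigators thought the topicals caused. The rule in Section 12 is written for a device study and does not name the products being compared.

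An investigator who follows the text with, say, a contact reaction to one of the topicals has to place it under device or procedure, or call it not related. Another investigator may read study agent as covering the topicals and mark it related. The related-event tables would then combine different judgements under one label. The reader could not tell whether a related event means an RF effect, a topical effect or either.

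**Working it through.** The documents give no adverse event rate, allocation ratio or error level for safety, so there is no figure to reproduce. The check is a reading of the passages against one another.

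**1. Do the two targets cover the topicals?**
- Device is restricted to effects of the device itself, so a reaction to a serum or gel falls outside it.
- Procedure covers activity in support of using the device. Under Section 11.2 the topicals go on after RF, and no lotion, gel or coupling medium is used during it. They are aftercare, and placing them under this definition is strained.
- Targets named: 2. Targets that name the randomised product: 0.

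**2. Does the relatedness scale fill the gap?** It refers to the study agent and its administration, which could include an applied product. Because the term is undefined, there are three readings for a topical reaction in the active arm:

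| Study agent read as | Coding of a topical reaction |
|---|---|
| RF device only | Related by timing alone, yet Not Related because another cause is established |
| Topicals only | Related, but with no matching target in the device/procedure list |
| Either | Related, and not separable from an RF effect |

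The first row shows an overlap. Read literally, the alternatives within each definition are joined by *or*, so one event can satisfy both. RF and the topicals are given at the same visit, so a local reaction soon afterwards has a temporal relationship to both.

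**3. What does treatment mean in the Section 14 tables?** The word has two uses:
- RF: the two treatment visits in Section 5 and the Treatment heading in Section 11.2.
- The topicals: the adjuvant combination treatment in Section 8, the topical study treatments in Section 10.2, and the treatment group set against standard of care in Section 14.

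The choice changes the table. If treatment means RF, related events can appear in both arms. If it means the topicals, the standard of care column is zero by construction. If it means either, the active column mixes two causes and the other column holds one.

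**4. How much of the safety output depends on this?** Section 14 lists overall TEAEs, severe TEAEs, related TEAEs, SAEs, related SAEs, and TEAEs leading to treatment discontinuation. Relatedness enters 2 of these 6. The other 4 need no causality judgement.

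**5. What is captured regardless?** The Section 12 definition of an adverse event applies whether or not the event is thought device related. Section 12 asks for a diagnosis where reasonably certain. Appendix C asks about changes in the treatment area, with free text. Under the Synopsis, TEAEs are summarised by group.

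**The case against.** The strongest case against is that this is a terminology gap, with the substance already covered. Topical reactions are recorded, can be named by diagnosis and are summarised by arm. Because both arms receive RF, a difference between arms bears directly on the topicals without any causality coding. The primary endpoint is a subject-rated Likert scale, and the secondary adverse event endpoint is incidence, so neither uses relatedness. The words study agent and treatment can be read to include the topicals. The Synopsis says SCR Complex is indicated for use immediately after the device, so even the procedure category is arguable. Finally, attribution to a topical in an open-label trial has no counterpart under standard of care.

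Most of this stands, and it limits the point. A reader might infer that harm from the topicals cannot be attributed or tabulated at all. The documents do not support that: the undefined terms leave room for attribution, and the by-arm summaries exist. Nor can one say that the adverse event case report form has no place for such an attribution, because that form is not in the documents. It would also go too far to call investigator attribution the main safety signal. The between-arm comparison has the randomised control, and the plan calls only for summary statistics on TEAEs, so there is no safety hypothesis test whose power could be at issue.

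What the objection does not remove is that Section 12 states a rule. Followed as written, the rule directs investigators away from the randomised product. Undefined terms that might rescue it are a poor basis for consistent coding at two centres.

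**Conclusion.** The point holds in a limited form. Event-level attribution to SCR Complex and Bio Cel is not provided for in Section 12, and the two related-event summaries in Section 14 cannot be read clearly as topical-related. They could merge RF and topical effects, or reflect different coding conventions at the two sites.

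The effect is confined to those two of six safety summaries. The tolerability endpoint, the VAS, adverse event incidence and the by-arm TEAE summaries are untouched. How many events would be miscoded cannot be estimated, because the documents give no rates for reactions to the topicals.

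The conclusion assumes that sites apply Section 12 as written and that no instruction outside these documents, such as case report form guidance, already defines the terms. It is worth correcting because the correction is cheap and the gap concerns the product under study.

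**What to change.** - **Section 12 and adverse event data collection:** add a third relatedness target, *Topical study product (SCR Complex / Bio Cel)*, recorded as not applicable for standard of care subjects. Ask for Related / Not Related separately for device, procedure and topical product.
- **Definitions:** state what study agent and treatment mean for each of the three targets, and use the terms consistently in Sections 12 and 14.
- **Section 14:** present all TEAEs by type and arm as the main safety comparison, carrying over the by-arm presentation that now appears only in the Synopsis. Tabulate related TEAEs and related SAEs by relatedness target and arm, labelled as supportive.

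The cost is one extra item per adverse event and a few lines of protocol text, with no added subjects or visits. The downside is that attribution to the topical is made open-label and has no standard of care comparator, so it supplements the by-arm comparison and does not replace it. The change should be in place before sites start coding events, since investigator causality is hard to reconstruct afterwards.
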